### **B1. PURPOSE OF PROTOCOL**

**Objective:** To disentangle the postprandial effects of blood glucose and insulin on brain activation in relation to a high glycemic index (GI) meal.

Patients with type 1 diabetes mellitus (T1DM) have elevated rates of dysregulated eating and obesity (1,2). We hypothesize that these phenomena are exacerbated by effects of insulin and downstream metabolites on brain areas involved in food craving; specifically the Nucleus Accumbens (NAcc). If true, high GI meals might trigger craving and overeating, as this diet is associated with higher insulin requirements. We will dissect the role of insulin vs. glucose in mediating brain activation in response to a high GI meal by applying high vs. low GI meals with optimal (euglycemic clamp) vs. matched (primed-variable infusion) insulin coverage.

**Aim 1: To examine the effects of insulin - in relation to a high GI meal - on brain activation and food intake in the early and late postprandial period.**

Hypotheses:

1. (Primary) In the late postprandial period (4 hrs postprandial), blood flow to the NAcc will be greater after a high vs low GI meal when differences in glycemia are prevented by insulin.
2. In the late postprandial period, functional connectivity of the NAcc and prefrontal and limbic areas of intake control will be higher after a high vs low GI meal when preventing differences in glycemia.
3. Subjective food craving and ad libitum food intake will be associated with NAcc blood flow and prefrontal-NAcc functional connectivity in the late postprandial period.
4. In the early postprandial period (1 hr postprandial), blood flow will be decreased in the hypothalamus in response to a high vs. low GI meal.

**Aim 2: To examine the effects of glucose - in relation to a high GI meal - on brain activation and food intake in the early and late postprandial period.**

Hypotheses:

5. In the late postprandial period, NAcc activation will not differ between the high and low GI meal when insulin exposure is matched, in spite of the resulting hyperglycemia.
6. In the late postprandial period, functional connectivity of the NAcc and prefrontal and limbic areas of intake control will be similar after a high vs low GI meal.
7. In the early postprandial period, hypothalamus blood flow will be lower after the high vs. low GI meal.
8. In the early postprandial period, functional connectivity between the NAcc and prefrontal and limbic areas involved in intake control will be higher after a high vs low GI meal.
9. Subjective food craving and ad libitum food intake will be associated with NAcc blood flow and prefrontal-NAcc functional connectivity in the late postprandial period.

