#### 4.4.1. Imaging

All imaging will be performed without contrast on the 3T scanner at the BIDMC research imaging facility (East Campus, Ansin 3). Participants will be asked to change into hospital gowns, to minimize the potential of unseen objects within pockets and metallic attachments to clothing. Participants will be instructed to lay still and rest with closed eyes during the image acquisition. They will then be positioned in a GE HD/X (GE Healthcare, Milwaukee, WI) in supine position. An imaging coil will be placed around their head. Participants will be given earplugs to minimize noise from the scanner and a squeeze ball that triggers an alarm to indicate a desire to exit. Participants will also be able to communicate by an intercom system to the operator. All scans will be performed by an experienced radiologic technologist.

Participants will undergo a 3 plane localizer, ASL and rs-fMRI scan at baseline, 1 hour and 4 hours postprandial. Between the baseline and 1-hour scan, an MPRAGE dataset will be obtained for anatomical correlation.

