The detectable effect for each paired-sample comparison (A vs B or C vs B) is  $(t\alpha/2 + t\beta) \times \text{SD}(D)/n^{1/2}$ , where n is the sample size, SD(D) is the standard deviation of the intrasubject difference in mean flow between conditions, and t() are Student deviates for power  $1 - \beta$  and two-sided type I error  $\alpha$  with  $n - 1$  df. Our prior study yielded  $\text{SD}(D) = 20$  units of blood flow. For these calculations we take  $\alpha = 0.05$  and a conservative value of  $\text{SD}(D) = 30$ . The planned sample of  $n = 15$  gives us 80% power to detect an effect of  $(2.1448 + 0.868) \times 30/15^{1/2} = 23.3$  units, or 4.3% of the mean flow (548 units in the prior study), and 90% power to detect an effect of 4.9%. These figures are comfortably below the 7.9% observed in our prior study. We therefore believe that the present protocol is adequately powered to detect clinically significant effects.

A still more conservative analytic plan (alternative #2) would be to apply the Bonferroni correction, halving the type I error rate for each of the two pre-planned comparisons. With this change, making  $\alpha = 0.025$ , the detectable effects are 4.8% with 80% power and 5.4% with 90% power. These figures are negligibly different from the earlier results.

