To address the primary and secondary hypotheses, we will employ methods appropriate to crossover trials. Hypotheses 1,2,4-8 will be tested by paired T-Test, controlling for baseline and meal order. Hypothesis 3 and 9 will be addressed by the Pearson correlation between brain activation parameters and calculated caloric intake. Secondary analyses of associations between brain activation, metabolic and psychophysical parameters will be performed using an ANOVA design. All tests will be conducted with a 5% Type I error rate. SAS software (Cary, NC) will be used for all computations.

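### Hypotheses 8 and 6 together imply that the glucose effect on NAcc connectivity fades between 1 h and 4 h, but the plan never estimates that change, and Hypothesis 6 can be supported only by a non-significant test with n = 15

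*Combined protocol and SAP*

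**What the plan says.** Aim 2 (B1, Purpose of Protocol) is "To examine the effects of glucose - in relation to a high GI meal - on brain activation and food intake in the early and late postprandial" phases. Section 2.2 (Test visits) assigns the glucose question to condition b versus condition c: matched insulin, different blood glucose.

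Two of the Aim 2 hypotheses concern the same measure and the same pair of conditions at different times:

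- Hypothesis 8, early period (1 h): "functional connectivity between the NAcc and prefrontal and limbic areas involved in intake control will be higher after a high vs low GI meal".
- Hypothesis 6, late period (4 h): "functional connectivity of the NAcc and prefrontal and limbic areas of intake control will be similar after a high vs low GI meal".

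The analysis is set out in Data Analyses: "Hypotheses 1,2,4-8 will be tested by paired T-Test, controlling for baseline and meal order". It adds: "All tests will be conducted with a 5% Type I error rate". The plan states no condition-by-time term, no contrast of the 1 h and 4 h condition effects, and no margin or interval rule for the word similar in Hypothesis 6. The ANOVA named in the same paragraph is for associations between brain, metabolic and psychophysical measures. The voxel-wise ANOVA described under Endpoints is for blood-flow images and specifies no time-by-condition term. The Multiple testing paragraph says that no power analysis was done for secondary outcomes.

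The data needed for a comparison over time will exist: "Participants will undergo a 3 plane localizer, ASL and rs-fMRI scan at baseline, 1 hour and 4 hours postprandial" (section 4.4.1).

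**The concern.** One significant test and one non-significant test do not show that two effects differ. If Hypothesis 8 is confirmed and the test of Hypothesis 6 is not significant, the natural summary is that glucose raises connectivity early and that the effect has gone by 4 h. That summary is about change over time, and no planned analysis examines change.

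The 4 h half of the summary is weak in its own right. With 15 men and no margin, a non-significant paired t-test cannot separate a negligible difference from one estimated too imprecisely to detect. The stake is how the Aim 2 connectivity results are interpreted, since that aim is framed around the early and late periods. The primary comparison is not at stake.

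**Working it through.** **1. The plan's own figure.** The power analysis uses n = 15, SD(D) = 30 units, two-sided alpha 0.05 and 14 df. The detectable effect is (2.1448 + 0.868) × 30/√15 = 23.3 units. Against a mean flow of 548 units this is 4.3%, as stated. In SD units it is 3.0128/√15 = 0.78 SD(D). The figure is for 4 h NAcc blood flow; the documents give none for connectivity.

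**2. Precision of one 4 h comparison.** The half-width of a 95% interval is 2.1448/√15 = 0.55 SD(D). Even an observed difference of exactly zero leaves true differences of up to 0.55 SD(D) in either direction within the interval.

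**3. How often a constant effect looks early-only.** Assumptions, because the documents give no values: normal c-b differences with equal SD at 1 h and 4 h; the same true effect at both times; correlation ρ between the two differences; and an effect size set to give the stated power at each time. Each time is tested by a two-sided paired t-test at 0.05 with n = 15. The pattern counted is 1 h significant in the predicted direction and 4 h not significant.

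At ρ = 0 the two tests are independent, so the rate is power × (1 − power): 0.5 × 0.5 = 25%, 0.8 × 0.2 = 16%, 0.9 × 0.1 = 9%. Simulation reproduces these and extends them to other correlations (at least 200,000 trials per setting):

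| Power at each time | ρ = 0 | 0.3 | 0.5 | 0.7 | 0.8 |
|---|---|---|---|---|---|
| 50% | 25% | 21% | 17% | 13% | 11% |
| 80% | 16% | 14% | 12% | 9% | 7.5% |
| 90% | 9% | 8% | 7% | 5.5% | 4.6% |

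Given that the 1 h test is already significant, a constant effect leaves the 4 h test non-significant in 27% to 50% of trials at 50% power, and in 11% to 20% at 80% power (ρ from 0.7 down to 0).

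**4. Adding the direct contrast.** For each man take (c-b at 1 h) minus (c-b at 4 h). Its SD is SD(D) × √(2(1 − ρ)). If the contrast must also be significant in the predicted direction, the false pattern falls to about 1% to 2% over 50% to 80% power and ρ from 0 to 0.7.

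**5. What the contrast costs.** With n = 15 the change detectable at 80% power is 0.78 × √(2(1 − ρ)) SD(D): 1.10, 0.92, 0.78 and 0.49 SD(D) at ρ = 0, 0.3, 0.5 and 0.8. The contrast is less precise than a single-time effect when ρ is below 0.5. Suppose Hypotheses 6 and 8 are exactly right: 80% power at 1 h and zero effect at 4 h. The two-test pattern then appears in about 76% of trials. Requiring the contrast as well lowers this to about 46%, 57%, 66% and 74% at ρ = 0, 0.3, 0.5 and 0.7.

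**6. What the contrast cannot show.** Let the 4 h effect be half the 1 h effect, with 80% power at 1 h and ρ from 0 to 0.7. All three conditions (1 h significant, 4 h not, contrast significant) are still met in about 16% to 31% of trials, although an effect remains at 4 h.

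**The case against.** The strongest reply is that the plan makes no claim of the kind at issue. Hypotheses 6 and 8 are separate predictions, each a condition difference at one time, and each is tested at that time. Aim 2 examines both periods; it does not say that they will be compared. This stands in part. A reader might infer that the plan contains a rule for declaring an effect early-only or late-only, and it contains none. What remains is that the two hypotheses, on one measure and one pair of conditions, jointly describe a change, and the plan offers nothing with which to judge it.

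A reader might also extend the point to the primary endpoint: that a late-phase NAcc flow effect cannot be claimed without a 1 h comparison, or that 1 h NAcc flow is left out of the analysis. The documents do not support either. Hypothesis 1 concerns 4 h and does not say that the effect is absent at 1 h. Section 2.2 explains that the late period is the main focus because compensatory mechanisms and potential overeating are expected then. The voxel-wise and regional blood-flow analyses under Endpoints name no time point and do not exclude 1 h, although no numbered hypothesis covers NAcc flow at that time.

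Two further objections stand and shape the fix. A contrast that excludes zero shows that the effect shrank, not that it is absent at 4 h. Requiring it also costs real detection when the hypotheses are true.

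**Conclusion.** The point holds as a limit on interpreting two secondary hypotheses. As planned, a significant Hypothesis 8 with a non-significant Hypothesis 6 would be weak evidence that the glucose effect on connectivity changes between 1 h and 4 h, and would not show that connectivity is similar at 4 h. Under an unchanged effect that pattern arises in about 9% to 25% of trials for 50% to 80% power and correlation 0 to 0.7, and in about 5% at the favourable end (90% power, correlation 0.8). These rates rest on assumed effect sizes, equal SDs and assumed correlations. The gap in the plan does not depend on them; only its size does.

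**What to change.** Add to Data Analyses:

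- As a secondary estimate for NAcc connectivity, the within-subject contrast (c-b at 1 h) minus (c-b at 4 h) with its 95% confidence interval, using the same baseline and order adjustment as the single-time tests. Specify that adjustment: baseline cancels exactly only for simple change scores, not when regression slopes differ between 1 h and 4 h.
- Hypothesis 6 reported as an estimate with its 95% confidence interval, and not called similar because a test was non-significant.
- A statement that the effect will be said to change between the early and late periods only if the contrast interval excludes zero. Add that this shows change and not absence at 4 h, and that a wide interval is inconclusive, not proof of a constant effect.

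A 4 h minus 1 h contrast for NAcc blood flow (a versus b) is optional. It is needed only if the report claims that the effect is specific to the late period.

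The cost is one added estimate from scans already planned, with no new visits or participants and no change to the primary test. The price is that a true early/late difference will be claimed less often, most of all if the 1 h and 4 h differences are weakly correlated.

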## **B2. SIGNIFICANCE AND BACKGROUND FOR THE STUDY**

### **1. OBESITY AND GLYCEMIC INDEX**

Childhood obesity has reached epidemic proportions, with even higher levels in individuals with T1DM (1). Though multi-factorial in origin, highly processed carbohydrates in general and glycemic index (GI) in particular have been hypothesized to play an important role. The GI is a system for classifying carbohydrate-containing foods according to glycemic response (3,4). A high GI meal produces rapid elevations in blood glucose and insulin levels, followed by a period of low availability of metabolic fuels and even reactive hypoglycemia (5-7). This situation results in hunger as the body attempts to restore energy homeostasis (8-10). While there is continuing controversy regarding the effects of GI on body weight in the general population (11), individuals with high insulin secretion seem to be especially susceptible to modifications in GI (12), suggesting a role of insulin in mediating the effects of GI.

### **2. GLYCEMIC INDEX IN TYPE 1 DIABETES**

[figure not shown]
With the rapid digestion of carbohydrate after a high GI meal, blood glucose peaks prior to achieving maximal insulin levels with standard therapy in individuals with T1DM. Insulin action may persist after nutrients from a high GI meal have been absorbed, resulting in an increased risk of hypoglycemia with subsequent need to eat carbohydrate to restore normal blood glucose. If this phenomenon recurs frequently, it could lead to excessive weight gain or possibly disordered/restrictive eating patterns in those who are attempting to avoid weight gain. Indeed, patients with T1DM have elevated rates of dysregulated eating and obesity (1,2). Several studies show benefits of GI in T1DM in terms of diet quality, postprandial hypoglycemia reduction and HbA1C (13,14). Because this diet lowers insulin requirement, there may be additional metabolic benefits including decreased anabolic drive at fat cells, and cerebral insulin signaling.

### **3. BRAIN CIRCUITS OF INTAKE CONTROL**

Neural substrates of intake control comprise a network of hypothalamus, basal ganglia and cortical, limbic and paralimbic regions involved in reward and emotional connotation. An area of particular interest is the NAcc, which plays a role in addiction and craving, and in integrating hedonic and homeostatic intake control via insulin and dopamine signaling. In rodents, microinjections of opiate into the nucleus accumbens increase food intake and the reward value of food (17). In humans, NAcc activation is associated with poor weight-loss outcomes (18), and activation is greater in obese vs. lean individuals after viewing or consuming palatable, high calorie food (19-24).

[figure not shown]
The NAcc may play a special role in the late postprandial phase after the high GI meal: In rodent studies, extracellular concentrations of dopamine increased more after consumption of short cake (high GI) compared to standard rodent chow (low GI) (25). In clinical studies, the NAcc has been shown to be activated by hunger, hypoglycemia, and high insulin levels (15,16), as encountered in response to a high GI meal.

#### 4. PRELIMINARY DATA

**FIGURE 2.** Mean  $\pm$  SE changes in plasma glucose (A), serum insulin (B), and hunger (C) after test meals. Differences between high- and low-glycemic index meals were significant at 4 h (the time point of interest) for all 3 outcomes by using paired *t* tests. *n* = 12.

We conducted a randomized controlled trial and demonstrated that a high GI meal, independent of palatability, caloric content or macronutrient composition, increased NAcc blood flow (a proxy of brain activation) in the late postprandial period in healthy overweight and obese participants (15).

**FIGURE 3.** Regions with significantly different cerebral blood flow 4 h after test meals ( $P \leq 0.002$ ). The color scale represents the value of the *t* statistic for the comparison between meals (*n* = 11) by using general linear model analyses as described in Subjects and Methods. For all areas depicted, the blood flow was greater after the high- than after the low-GI meal. GI, glycemic index.

Unresolved scientific questions involve (1) whether changes in blood glucose *per se* or the associated higher insulin levels mediate NAcc activation and the likely adverse downstream effects, and (2) how interactions with other areas of intake control are affected. While glucose and insulin both have direct effects on the brain, we hypothesize that insulin is the primary driver in this context (15,16). As both parameters are tightly correlated in healthy participants, this could not be addressed in our original study. T1DM is an ideal experimental setting to disentangle these two influences.

#### 2.5. SIGNIFICANCE

We aim to disentangle the effects of variations in blood glucose and insulin on brain function in the postprandial state among youth with T1DM. The outcome of this work would have not only scientific but also clinical implications. If NAcc activation and its likely adverse effects are mediated by glucose excursion, optimal insulin coverage should be sufficient to prevent this problem. If it is mediated by insulin or its downstream effects, however, a high GI diet might trigger craving and overeating despite optimal insulin coverage. Thus, our findings will point the way to a heightened focus on improved insulin delivery to optimally control blood glucose *versus* measures to decrease insulin demand, including a low GI diet.

## B3. DESCRIPTION OF RESEARCH PROTOCOL

### A. Study Design – Overview, Methods, Procedures

#### **Brief Overview of the Study**

##### **1. Overall Study Design and Research Question**

This is an experimental study in humans using a randomized, double-blinded cross-over design to examine the effects of glucose and insulin on brain activation in relation to a high glycemic index (GI) meal in the early and late postprandial period.

##### **2. Key Details of Study Implementation**

Male participants with Type 1 diabetes will be enrolled to participate in 4 study visits involving standardized test meals and iv insulin infusions. Participants will be enrolled for 1-3 months. The primary endpoint is blood flow in the NAcc, a brain area that regulates food intake and craving.

##### **3. Summary of Study Procedures**

A total of 15 male participants (age 18-45) with T1DM will be recruited. Participants will be enrolled in the study for a total of 1-3 months, and participate in a pre-test visit and three test visits, each after a 10-12-hr overnight fast. Participants will be instructed to consume their regular, weight maintaining diet between visits.

At the **pre-test visit**, the study director or PI will meet participants at the BIDMC GCRC, confirm eligibility and obtain informed consent. Participants will receive a low GI meal with optimal iv insulin coverage using a negative feedback algorithm to maintain euglycemia (euglycemic clamp). Insulin requirement will be quantified. At some time during the visit, participants will present to the BIDMC research imaging facility (East Campus, Ansin 3) for a practice MRI session, during which they will undergo a brief imaging sequence to get accustomed to the scanning process and eliminate anxiety as a confounder of imaging data.

At each of **3 test visits** at the BIDMC GCRC and research imaging facility (East Campus, Ansin 3), one of the following experimental conditions will be applied in a randomized, blinded cross-over design: (a) high GI meal with euglycemic clamp, (b) low GI meal with euglycemic clamp, (c) high GI meal with primed-variable insulin infusion at the rate established during the pre-test visit. After steady state is established, baseline laboratory evaluation and MRI imaging will be obtained, followed by the test meal. Imaging will be repeated at 1 and 4 hours postprandial. Blood samples for pertinent metabolic and hormonal parameters will be obtained every 30 minutes. Each test-visit concludes with a standard weighed meal to quantify ad-libitum intake.

#### **Detailed Study Procedures**

##### **A Pilot Phase**

The pilot phase serves to establish feasibility of the insulin clamp and finalize clamp protocol in the setting of the test meals. 1-3 subjects will be recruited to undergo 3 test visits as outlined below, but no pre-test visit. Meal administration and insulin infusions with blood glucose checks will be as outlined. The order of visits will condition a → condition b → condition c and will not be randomized. The insulin dose administered during condition c will be determined during condition a.

Pilot phase subjects will undergo venous blood sampling for HgbA1C (once per visit) and C-peptide (once per study) only and will not undergo imaging. The same inclusion and exclusion criteria will apply for pilot phase subjects with the exception that the MRI compatibility exclusion criterion will be waved.

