### 2.1. Pre-test visit

The study director or PI will meet participants at the BIDMC GCRC, confirm eligibility and obtain informed consent. Participants will receive a low GI meal with optimal iv insulin coverage using a negative feedback algorithm to maintain euglycemia (euglycemic clamp), as outlined in 3.3.1.. Insulin requirement will be quantified. At some time during the visit, participants will be transferred to the BIDMC imaging facility for a 5-minute practice MRI session, during which they will be positioned in the scanner and undergo a brief imaging sequence to get accustomed to the scanning process and eliminate anxiety as a confounder of imaging data. Insulin infusion may be briefly discontinued while in the MRI scanner.

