### 2.2. Test visits

In a double-blinded cross-over design, three test visits will serve to evaluate brain function, metabolic, and hormonal parameters. Sessions will be at least 1 week apart to eliminate habituation to the scanning process and carry-over effects, but no more than 4 weeks apart to limit intra-subject variability. At each test visit at the BIDMC GCRC and imaging facility, one of the following experimental conditions will be applied in a randomized, blinded cross-over design: (a) high GI meal with euglycemic clamp, (b) low GI meal with euglycemic clamp, (c) high GI meal with primed-variable insulin infusion at the rate established during the pre-test visit. As the high GI meal is associated with higher insulin requirement, this condition will result in moderate hyperglycemia. Thus, the design will allow comparison between a high and low GI meal with matched blood glucose but different insulin levels (condition a vs. b) **or** matched insulin with different blood glucose levels (condition b vs. c) (figure 1). After steady state insulin infusion is achieved, baseline laboratory studies will be obtained and participants will be transferred to the BIDMC imaging facility for their baseline scan. Postprandial imaging times are chosen to study cerebral blood flow and functional connectivity between brain areas of interest at the peak of blood glucose and insulin requirement (+1 h) and at the nadir of blood glucose/ insulin (+4 h). Because compensatory mechanisms and potential overeating are expected in

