#### 3.3.1.2. Low GI meal (screening visit and condition b)

After consumption of the test meal, insulin infusion rate will be increased by 0.1-0.2 mU/kg/min every five minutes until blood glucose starts to fall, with further adjustments based on blood glucose trajectory. We then anticipate a stepwise decrease in insulin infusion rate, reaching basal rates at 3 hours postprandial. Blood glucose sampling and insulin infusion will be continued according to a negative-feedback mechanism. for 4 1/2 hours postprandial. Then insulin infusion will be discontinued and insulin pump therapy resumed according to the participants' home regimen using their own equipment.

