#### **Insulin administration chart**

Planned insulin infusion rates to account for meals are depicted. Rates may vary based on individual insulin requirements and measured blood glucose as outlined above.

Time (minute)	Insulin infusion rate (mU/kg/min)	
	HGI	LGI
pre-meal	0.2	0.2
5	0.5	0.3
10	0.8	0.5
15	1.1	0.6
20	1.4	0.8
25	1.2	0.8
30	1.1	0.7
35	1.0	0.7
40	0.8	0.7
50	0.8	0.6
70	0.8	0.4
100	0.7	0.5
130	0.5	0.4
160	0.3	0.4
200	0.2	0.3
220-end	0.2	0.2

Example: Based on this chart, the total meal insulin administered for an 80 kg male would be 8 units for the high GI and 5 units for the low GI meal. These are customary amounts of mealtime insulin.

Due to individual differences in insulin requirement, actual administered rates of insulin will vary between 0.1 and 2.5 mU/kg·min. For patient safety, rates outside this specified range may be necessary at times.

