**3.3.2. Primed-variable insulin infusion - experimental condition c (figure 1)**

In the run-in period, glucose levels will be measured every 5 minutes. A basal insulin infusion will be initially administered at 80% of the patients insulin pump basal rate, and will be adjusted between 0.1 and 2.5 mU/kg·min, depending upon the patient’s plasma glucose level in relation to the target range target of 90-100 mg/dl. Once steady state is achieved, baseline laboratory studies and imaging will be obtained and test meal administered. Then, a primed-variable infusion of insulin will be administered at the rate established during the pre-test visit to achieve similar plasma insulin levels. For patient safety, glucose levels will be measured every 30 minutes. If glucose levels are > 400 mg/dl or < 60 mg/dl, insulin infusion will be adjusted to maintain glucose levels target of 60-400 mg/dl. Insulin infusion will continue for 4 1/2 hours postprandial. Then, Insulin infusion will be discontinued and insulin pump therapy resumed according to the participants’ home regimen using their own equipment.

[figure not shown]

Figure 1:

**Figure 1: Schematic depiction of anticipated glycemic changes and insulin levels during the different experimental conditions.** Theoretical glycemic response to the meal is plotted in gray, anticipated insulin requirements in blue and resulting blood glucose in green. (a) High GI meal with euglycemic clamp, (b) low GI meal with euglycemic clamp, (c) high GI meal with primed-variable insulin infusion at the rate established during the pre-test visit. As the high GI meal is associated with higher insulin requirement, this condition will result in moderate hyperglycemia. Thus, the design will allow comparison between a high and low GI meal with matched blood glucose but different insulin levels (experiment 1 - condition a vs. b) **or** matched insulin with different blood glucose levels (experiment 2 - condition b vs. c)

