**4.3. Process measures**

[figure not shown]
- Fasting C-peptide via CLIA certified methods at the pre-test visit.
- Point of care blood glucose will be checked every 5 minutes during the pre-test visit and conditions a and b. Glucose checks will be spaced out to every 30 minutes after administration of the test meal during condition c.

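### The pilot takes condition c's insulin dose from the high GI clamp (condition a), but condition c requires the dose from a low GI clamp (condition b)

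*Combined protocol and SAP*

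**What the plan says.** All references are to the combined protocol and SAP.

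- **A Pilot Phase.** One to three subjects attend three test visits and no pre-test visit. "The order of visits will condition a → condition b → condition c and will not be randomized". On dosing: "The insulin dose administered during condition c will be determined during condition a". The same section says that meals, infusions and glucose checks otherwise follow the main procedures.
- **3.3.2 (condition c).** After the high GI meal, "a primed-variable infusion of insulin will be administered at the rate established during the pre-test visit to achieve similar plasma insulin levels".
- **2.1 Pre-test visit.** "Participants will receive a low GI meal with optimal iv insulin coverage using a negative feedback algorithm". This visit supplies the rate that condition c uses.
- **3.3.1.2.** The heading reads "Low GI meal (screening visit and condition b", so the pre-test visit and condition b share one clamp procedure.
- **2.2 Test visits.** Condition a is the high GI clamp and condition b the low GI clamp. On the effect of condition c: "As the high GI meal is associated with higher insulin requirement, this condition will result in moderate hyperglycemia". The b versus c comparison is meant to have equal insulin and unequal glucose.
- **B. Statistical Considerations, power analysis.** Condition C is labelled as high GI, low insulin and high glucose.

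**The concern.** The source of the insulin rate is what distinguishes condition c from condition a, because both use the high GI meal. If c takes its rate from a low GI clamp, the meal is under-covered, insulin matches b, and glucose rises. If c takes its rate from a, the subject gets the same meal with the insulin that held glucose in range at visit a. That is a repeat of a with the feedback removed.

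The sentence is an operative dosing rule for the pilot subjects. If staff follow it, visit c still exercises the mechanics of a preset infusion. It cannot show how large the hyperglycemia is under the real condition c, or whether glucose approaches the 400 mg/dl intervention limit, before 15 participants undergo it. Pilot subjects would also receive the larger dose under sparser monitoring: "Glucose checks will be spaced out to every 30 minutes after administration of the test meal during condition c", compared with every 5 minutes during the clamps.

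**Working it through.** **Step 1: which visit supplies condition c's rate?**

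| | Test phase | Pilot as written | Pilot following the definition of c |
|---|---|---|---|
| Meal at visit c | high GI | high GI | high GI |
| Visit that sets c's rate | pre-test (3.3.2) | condition a | condition b |
| Meal at that visit | low GI (2.1, 3.3.1.2) | high GI (2.2) | low GI (2.2, 3.3.1.2) |
| Insulin matched to b? | yes | no | yes |
| Expected glucose at c | moderately high (2.2) | near the clamp range | moderately high |

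With no pre-test visit, the pilot's only low GI clamp is condition b. The fixed order a, b, c makes b's rate available before visit c, so scheduling does not force the use of a. No section gives a reason for choosing a.

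**Step 2: how different are the two doses?**

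This step is illustrative, because actual doses come from each subject's own clamp. The protocol's example is "total meal insulin administered for an 80 kg male would be 8 units for the high GI and 5 units for the low GI" meal: a ratio of 8/5 = 1.6 and a difference of 3 units.

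To check this, I integrated the insulin administration chart from 0 to 220 minutes, with the pre-meal rate of 0.2 mU/kg/min at time 0.

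- Total = sum of (rate × interval length).
- Basal = 0.2 × 220 = 44 mU/kg.
- Meal insulin = total − 44.
- Units at 80 kg = mU/kg × 80 / 1000.

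With each rate held until the next time point:

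- High GI, 0–40 min: 5 × (0.2 + 0.5 + 0.8 + 1.1 + 1.4 + 1.2 + 1.1 + 1.0) = 36.5. From 40 min: 8 + 16 + 24 + 21 + 15 + 12 + 4 = 100. Total 136.5.
- Low GI, 0–40 min: 5 × (0.2 + 0.3 + 0.5 + 0.6 + 0.8 + 0.8 + 0.7 + 0.7) = 23. From 40 min: 7 + 12 + 12 + 15 + 12 + 16 + 6 = 80. Total 103.0.

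The chart does not say how to read the rates between time points, so two other rules are shown as well.

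| Rule | Total, high vs low GI (mU/kg) | Ratio | Above basal (mU/kg) | Ratio | Meal insulin at 80 kg (U) | Difference (U) |
|---|---|---|---|---|---|---|
| Rate held to next time point | 136.5 vs 103.0 | 1.33 | 92.5 vs 59.0 | 1.57 | 7.4 vs 4.7 | 2.7 |
| Trapezoid | 128.5 vs 98.75 | 1.30 | 84.5 vs 54.75 | 1.54 | 6.8 vs 4.4 | 2.4 |
| Rate applied to preceding interval | 120.5 vs 94.5 | 1.28 | 76.5 vs 50.5 | 1.51 | 6.1 vs 4.0 | 2.1 |

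The first rule comes closest to the protocol's 8 and 5 units; all three fall slightly below. Under every rule the high GI dose above basal is about one and a half times the low GI dose.

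**The case against.** The strongest reply is that little depends on this sentence. It governs one to three non-randomized subjects without imaging. The pilot's stated purpose is to show that the clamp is feasible and to settle its protocol; conditions a and b are the clamps, and they are piloted either way. Measuring the hyperglycemia of condition c is not a listed pilot objective. Venous sampling in the pilot covers only HbA1c and C-peptide, so even the corrected pilot could not confirm that plasma insulin in c matches b. All of this stands, and it limits the consequence. It does not make the sentence right: the pilot spends a full visit on condition c, and as written that visit delivers something else.

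A second reply is that the pilot section sends staff to the main procedures for infusions, which would lead them to the correct rate. But the specific sentence overrides the general pointer. The two conflict, and the reader is not told which prevails.

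On safety, the reply largely succeeds. The larger profile was titrated in the same subject on the same meal. Section 3.3.2 requires adjustment below 60 or above 400 mg/dl, and B5 provides iv dextrose. The 30-minute checks apply to condition c whichever dose is used. The literal reading would also be expected to produce less hyperglycemia than the intended one.

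**Conclusion.** The concern holds: the dosing sentence contradicts the protocol's own definition of condition c. Followed as written, pilot visit c would give roughly 2 to 3 units more meal insulin at 80 kg than the definition implies, and the hyperglycemic condition would go unpiloted. The size rests on the protocol's example and chart, and individual doses will differ. The contradiction itself depends on no arithmetic.

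The scope is narrow. Test-phase participants get their rate from their own pre-test visit, so the a versus b and b versus c contrasts, the analysis and the power calculation are untouched. It should be corrected because it is a dosing instruction, and the correction is nearly free.

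**What to change.** Before the first pilot subject, change the sentence in 'A Pilot Phase' so that condition c's insulin dose is determined during condition b. This is a one-letter change. Visits, order, subjects and procedures stay as they are.

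If the sponsor does intend condition a as the source, the section should say so, give the reason, and state that the pilot's visit c is not the condition c used in the test phase.
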